We propose to obtain consent from a total of 200 participants in order to identify 48 who meet all inclusion and exclusion criteria and complete all aspects of the study. During a phone screening interview, the study will be described in detail and preliminary participant characteristics (e.g. age, number of cigarettes per day) will be assessed. Those participants who meet criteria for participation will be invited to our offices for an informed consent and screening visit.

Screening session. During screening, all aspects of the study will be described to subjects and informed consent will be acquired. Breath and saliva samples will be collected in order to verify smoking status and blood alcohol level (BAL); and measures including, but not limited to, smoking

history, nicotine dependence, and mood will be collected. Vitals such as heart rate, blood pressure and weight/height will also be measured. Urine samples will be obtained in order to screen for illicit drug use and pregnancy status. Use of illegal drugs will be exclusionary. Marijuana use will not be exclusionary, but participants must agree to not use marijuana 24 hours prior to sessions and may not mix their marijuana with tobacco (i.e. blunts). Females who test positive for pregnancy will be excluded from the study and be given options for smoking cessation programs. Participants will also be interviewed regarding their smoking behavior including an assessment of contexts (places) in which they smoke and abstain from smoking cigarettes.

Inclusion criteria:

- 1) generally healthy [(i.e. ambulatory, not currently sick)]
- 2) between the ages of 18 and 65
- 3) smoking of at least 5 cig/day of a brand delivering ≥ 0.5 mg nicotine (FTC method) for ≥ 1 year
- 4) an expired CO concentration of at least 10 ppm (to confirm inhalation) or urinary cotinine >1000 ng/mL (NicAlert = 6).
- 5) interest in quitting smoking within the timeframe of the experiment.
- 6) ability to identify 4 personal smoking and 4 personal non-smoking places.
- 7) right handed as measured by a three-item scale used in our laboratory
- 8) own a smartphone
- 9) Breath Alcohol Level =0.000

Exclusion criteria:

- 1) immediate or no desire to quit smoking;
- 2) inability to attend all required experimental sessions;
- 3) use of other tobacco products or e-cigarettes more than 9 days in the past 30 days;
- 4) current alcohol or drug abuse;

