MetricWire Mobile Application: Following the picture review, participants will be trained on how to download and use MetricWire, a mobile application (app) on a smartphone and how to answer study related questions on the app. After the Camera Turn-in session participants will be randomly prompted to answer questions, including items related to craving and mood, on the mobile app up to 6 times throughout the day. Participants will also be asked fill out a survey on the app each time they smoke a cigarette. Participants will be compensated \$0.50 for each of the 6 prompted surveys completed (\$3.00 maximum daily amount)

GPS Logger- Participants will carry a GPS device with them for two weeks prior to the quit date and two weeks after the quit date. The GPS logger is a small device designed to measure and record location by triangulating signals transmitted from earth orbiting satellites. The unit we will use is about the size of a cigarette lighter and is rechargeable. When operational, the GPS unit will continuously record participant location and this information will be later downloaded onto a secured server with limited access. Participants will be required to keep the GPS on and with them at all times during the 4 week period except when it might become wet (bathing, showering, swimming) or when sleeping. Participants

will be provided with detailed instructions on how to operate and recharge the unit. Participants will receive \$2.50 per day for carrying the device and providing high quality GPS tracking (i.e. no evidence of leaving it in one location for the entire day). Participants will also receive a \$75 bonus for 4 weeks of compliance with GPS tracking and MetricWire surveys.

Nicotine Patches:

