fMRI session. Following the picture taking phase, 1 fMRI session will take place. The fMRI session will begin following 24 hour smoking abstinence. 24 hour smoking abstinence will be verified by breath CO <6ppm. Female participants must provide a urine sample for pregnancy testing the day of the MRI scan. The test results must be negative in order to continue with the study. Prior to entering the scanner, participants will complete questionnaires regarding their current mood and withdrawal symptoms. Respiration and heart rate will be monitored during the scan to collect physiological data. Standard localizer and anatomical scans will be conducted followed by fMRI scanning. During fMRI scanning, participants will view pictures of personal and standard smoking and non-smoking environments; and also pictures of smoking-related (cigarettes, lighters, ashtrays) and non-smoking related objects (keys, tape dispensers, pencils). Participants will also complete a Go/Go/No-Go task consisting of three types of trials: frequent-Go, infrequent-Go, and No-Go trials. In the frequent-Go and infrequent-Go trials, subjects are required to press a button as quickly as possible, whereas in the No-Go trials, subjects are to refrain from pressing the button. For each trial, a colored circle is presented. The color of the circle indicates the type of trial: gray indicates a frequent-Go trial, and yellow or blue indicates the infrequent-Go or No-Go trial. The relationship between color (yellow/blue) and trials type (infrequent-Go/No-Go) is counterbalanced across subjects. After being removed from the scanner, participants will complete post-session mood and withdrawal questionnaires.

Breath alcohol levels will be assessed prior to the fMRI session and participants must record a BAL of 0.000. Participants who test positive for alcohol will be excluded from participation that day and asked to reschedule. Participants testing positive for alcohol on more than one occasion will be excluded from the study.

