Our EMA+GPS analysis will primarily focus on locations where smokers smoke before and after quitting smoking. We will first examine whether post-quit craving and lapse behavior occur in locations associated with smoking prior to quitting smoking. Moreover, we will evaluate whether being in locations associated with prior smoking (but not smoking) during the post-cessation period are associated with better treatment outcomes. Finally, based on GPS location and self-reported EMA location, we will assign smoking intensity values to personal smoking environments presented in the scanner. We will evaluate whether EMA-assessed smoking intensity values are correlated with brain responses to these personal smoking environments.

RISK/BENEFIT ASSESSMENT

Nicotine Patch: Insomnia and abnormal dreams are common and expected side effects associated with 24 hour nicotine patches. If a subject complains of disturbed sleep, he or she will be instructed to remove the patch at bedtime and apply a new one the next day at the usual time. Skin irritation may occur, although this will be minimized by changing the site of patch application daily. Using 1% hydrocortisone cream on the affected area will be recommended to help reduce skin irritation. If a subject develops itching or a rash at the patch site, he or she will be advised to use 1% hydrocortisone cream on the affected area. Symptoms associated with nicotine toxicity include, lightheadedness, dizziness, nausea, fainting and vomiting. Symptoms considered moderate to severe in nature will be evaluated by the study medical staff by telephone or in person, depending upon the level of severity. Upon evaluation, the subject will then be given the choice of continuing in the study while discontinuing patch use.

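### The 24-hour abstinence rule before the scan, checked only by breath CO, does not cover e-cigarettes or smokeless tobacco, although eligibility admits their use on up to 9 days in 30

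*Combined protocol and SAP*

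**What the plan says.** **Entry.** Exclusion criterion 3 rules out "use of other tobacco products or e-cigarettes more than 9 days in the past 30 days". Use on 1 to 9 days is therefore allowed. The criterion looks back from screening, and nothing later in the document limits these products. Current users of nicotine replacement or other cessation treatment are excluded separately (criterion 7).

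**Scan condition.** Under fMRI session: "The fMRI session will begin following 24 hour smoking abstinence", and "24 hour smoking abstinence will be verified by breath CO <6ppm". No nicotine or cotinine measurement is named for that day. Mood and withdrawal questionnaires are completed before the scan.

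**Other substances.** The Screening session text says "participants must agree to not use marijuana 24 hours prior to sessions". The fMRI session text requires a zero breath alcohol reading and reschedules a participant who tests positive.

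**Use of the scan.** Data Analysis correlates the brain response (smoking minus non-smoking environments) with days to lapse and days to relapse. It also states: "We will evaluate whether EMA-assessed smoking intensity values are correlated with brain responses to these personal smoking environments".

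**The concern.** The Purpose section presents the scan as a measure of brain reactivity after 24 hours of abstinence. That needs participants to arrive in a broadly similar nicotine state. The plan admits some people who use nicotine products other than cigarettes, asks everyone not to smoke for a day, and verifies this with a test that cannot see two of the permitted sources. A participant who vapes or uses smokeless tobacco through the 24 hours breaks no written rule and would not be identified.

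The analysis most exposed is the between-person one. If nicotine state at the scan varies from person to person and is not recorded, it adds noise to the correlation with days to lapse and relapse. If those who substitute another product also differ in dependence or lapse risk, it could confound that correlation. Without a record of use, the analyst cannot examine either possibility afterwards.

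**Working it through.** **1. Text comparison.** The documents give no prevalence of dual use and no power calculation behind the 48 completers, so there is no stated figure to reproduce.

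| Substance | Allowed at entry? | Rule before the scan | Check at the scan |
|---|---|---|---|
| Cigarettes | Yes (required) | 24 h abstinence | Breath CO <6 ppm |
| Other combusted tobacco | Up to 9 of 30 days | Falls within smoking abstinence | CO, if recent |
| E-cigarettes, smokeless tobacco | Up to 9 of 30 days | None stated | None stated |
| Marijuana | Yes | 24 h without use | None stated |
| Alcohol | Yes, short of abuse | Zero reading on the day | Breath alcohol; reschedule |

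The third row is the gap. The withdrawal questionnaire captures symptoms but, as described, does not ask which products were used.

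**2. Rate of use at the limit.** 9/30 = 0.30 of days. Over the 14 pre-quit days, a participant continuing at that rate would have 14 × 0.30 = 4.2 use days.

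**3. Scans that follow a use day.** Let *q* be the share of completers who use other products and *d* their use days per 30. If use is unrelated to the scan date, the expected number is 48 × *q* × *d*/30. The 48 and the cap of 9 come from the protocol; *q* and *d* = 4 are assumptions.

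| *q* | *d* = 4 | *d* = 9 |
|---|---|---|
| 10% | 48 × 0.10 × 4/30 = 0.6 | 48 × 0.10 × 9/30 = 1.4 |
| 25% | 48 × 0.25 × 4/30 = 1.6 | 48 × 0.25 × 9/30 = 3.6 |
| 50% | 48 × 0.50 × 4/30 = 3.2 | 48 × 0.50 × 9/30 = 7.2 |

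These counts include combusted products, some of which CO would catch, so they overstate the unverified part. Substitution during the enforced day without cigarettes would push the other way, by an amount the documents do not allow one to estimate.

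**4. Rough effect on a correlation.** Assume a two-sided alpha of 0.05 and the Fisher z approximation. With *n* = 48, the correlation detectable with 80% power is tanh[(1.96 + 0.84)/√45] = 0.395. As a crude worst case, let a fraction *f* of scans carry no signal, so that the correlation becomes 0.395 × (1 − *f*). The *d* = 9 column gives:

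| *f* | Diluted correlation | Power |
|---|---|---|
| 1.44/48 = 3% | 0.383 | 77% |
| 3.6/48 = 7.5% | 0.365 | 73% |
| 7.2/48 = 15% | 0.336 | 65% |

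This shows scale only. A scan in a replete state need not lose all its signal, and the calculation says nothing about confounding.

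**The case against.** The best defence is that the gap is narrower than it looks. Several stronger readings are tempting and should be set aside.

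- *The washout covers cigarettes only.* A reader might infer this, but the requirement is smoking abstinence checked by CO. That takes in cigars and other smoked products. Only e-cigarettes and smokeless tobacco remain.
- *Nicotine state is wholly uncontrolled.* It is limited at entry by the 9-day cap and the exclusion of nicotine-replacement users, and withdrawal symptoms are recorded before the scan. None of this identifies product use in the preceding 24 hours.
- *The diary is defective because its event survey is triggered only by cigarettes.* The instruction does read "Participants will also be asked fill out a survey on the app each time they smoke a cigarette". However, the stated exposure is smoking by place. A place where someone vapes but seldom smokes should get a low smoking-intensity value, so that is correct coding.
- *Vaping after the quit day leaves no record and spoils the lapse analysis.* The prompted surveys are described only openly: participants are "randomly prompted to answer questions, including items related to craving and mood, on the mobile app up to 6 times throughout the day". An item on other products is therefore not ruled out. Patches supply nicotine after quitting by design, and vaping does not change where a smoking lapse took place.
- *A large share of completers use at the cap.* Nothing in the documents supports any particular share.

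It is also fair to say that the main brain measure is a within-person contrast from a single scan, so nicotine state is common to both sides of it. That state could still alter the size of the contrast, and the contrast is then compared between people. The defence narrows the point, but does not supply a pre-scan rule or a record for e-cigarettes and smokeless tobacco.

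**Conclusion.** The concern holds for the scan condition and does not extend to the diary. As written, the rule and its CO check would pass a nicotine-replete user of e-cigarettes or smokeless tobacco into a scan meant to measure abstinent cue response. Marijuana and alcohol each have an explicit pre-scan rule. The consequence is added noise and possible confounding in the correlations with days to lapse and relapse.

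The likely size is small to moderate: about 0.6 to 7 of 48 scans. This rests on assumed shares of 10% to 50%, 4 to 9 use days in 30, and use unrelated to the scan date. It also takes the scan to be made without a patch. The patch section gives no start date, but its total of 6 + 2 + 2 = 10 weeks matches the post-quit follow-up. The point should be fixed because the remedy is cheap and the information cannot be reliably recovered later. It does not invalidate the design.

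**What to change.** 1. In the fMRI session section, define the 24-hour pre-scan condition as no cigarettes, e-cigarettes or any other tobacco product. Keep the CO check for the combusted part.
2. Add one self-report item on use of these products in the past 24 hours to the questionnaires already completed before the scan.
3. Reschedule the scan when use is reported, as the plan already does for a positive alcohol reading. At minimum, keep and flag such scans and prespecify a repeat of the brain-response analyses without them.

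The cost is one protocol sentence, one questionnaire item and a few rescheduled scans. The item relies on self-report, and a participant who expects to be rescheduled may under-report.

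The event-survey trigger need not change. Recording other-product use in the diary is optional, because the plan's stated exposure is smoking by place.

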EFFECTS OF SMOKING ENVIRONMENTS ON BRAIN REACTIVITY

Principal Investigator:

F. [name].

Co Investigator:

[name].

PURPOSE

The goal of this study is to evaluate correlations between brain reactivity (as assessed via fMRI following 24-h abstinence) and the amount of smoking in a specific location. We will use ecological momentary assessment (EMA) to ask smokers to rate their exposure to, and smoking in, specific personal smoking environment cues (PSEs) over the course of 2 weeks before quitting smoking and 2 weeks after quitting smoking. Establishing that such correlations exist will provide strong evidence on the functional neuroanatomy of drug-context memory formation and retrieval.

BACKGROUND

Encountering an environment in which smoking has regularly occurred and/or its effects experienced, triggers strong craving and promotes lapse or relapse in smokers who have quit. Clinicians and recovery programs have long recognized the powerful influence of drug-environment associations and counsel patients to avoid “people, places, and things” associated with prior use. Confirming these intuitions, real-world assessment (i.e. ecological momentary assessment) of smoking suggests that relapse most often occurs in environments previously associated with smoking and that abstaining in contexts associated with smoking decreases the probability of later lapse.

Despite recognition of the influence of environment as a determinant of drug use and relapse, and despite a large and growing preclinical literature, surprisingly little empirical work has specifically addressed questions around drug-environment associations in humans. Laboratory-based studies have demonstrated that environments previously unassociated with smoking, when paired with or made predictive of smoking, can elicit urges to smoke. More recently, preference for a room paired with a low dose of amphetamine has been demonstrated in amphetamine-naïve subjects and has been suggested as a human analog of conditioned place preference (CPP). Collectively, this and other cue-conditioning research in humans provides insight into the formation of drug-environment associations but leaves open questions regarding the influence of *real-world environments* on subjective experience, behavior and brain function among individuals with long drug use histories.

DESIGN AND PROCEDURES

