Lab Visits: Four lab visits will be conducted during the 10 weeks following the quit day. The visits will take place 1 week, 2 weeks, 6 weeks and 10 weeks post quit day. Each visit will have a window period of +/- 3 days from targeted date, calculated from date of camera return visit. Visits exceeding the window period will be recorded as a protocol deviation. These visits will be largely identical except that instructions and reminders to participants about upcoming events will vary from session to session. At each lab visit the following will be collected: vitals (heart rate, blood pressure and weight), breath CO and measures of smoking withdrawal and mood. Nicotine patches and instructions for using them will

be provided at each session. Advice on quitting and minimal support will be provided as requested at these visits. During the third lab visit participants will review and annotate their GPS tracks with study staff by indicating the name (e.g. home, work, library) of stay-points (i.e. places they spent more than 1 hour). Each lab visit will require 20-30 minutes of participant time.

6 month Follow-Up phone call. Participants will be contacted by phone 6 months after completing the study to complete a brief interview about current smoking status and nicotine dependence.

DATA ANALYSIS

The primary aim of the study is to examine differences in brain responses to personal vs. standard smoking and non-smoking environments. Multiple methods will be used to test hypotheses about brain functioning during cue-reactivity (CR): a region of interest (ROI) based approach for testing specific *a priori* hypotheses and a voxel-wise whole-brain analysis for identifying unexpected findings. This two-pronged approach to fMRI data analysis will allow us to maximally evaluate variability in signal over space and time while minimizing the risk of both Type I and II error. For each hypothesis, the brain CR variable of interest will be the difference in mean % signal change. We will examine correlation between brain responses to smoking environments (minus non-smoking environments) and smoking cessation outcomes (i.e. days to lapse, days to relapse).

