We will advertise in local newspapers, the radio, tv, flyers on bulletin boards, Facebook and on the internet (including but not limited to trianglesmokingstudies.com and craigslist). When we receive calls from potential subjects we will return their call and ask information including name, address, age, and smoking history. They will be given a brief description of our studies and will be asked questions to determine interest and eligibility. If they do qualify we will schedule a screening session where we will follow all IRB protocols of informed consent.

We will utilize medical records querying systems to identify and pre-screen possibly eligible subjects. After a report is generated from the medical records of patients meeting our defined criteria, they will be sent an invitation to participate in the study through their Duke patient portal. Patients can indicate on the portal whether or not to seek more information about the study which will send a communication to the research team. Those who indicate interest in participating will be contacted by the research team to proceed to the initial phone screening phase (as described above).

Participants will receive \$25 at the screening session if they pass the drug test, breath alcohol test and CO test. Individuals who do not pass these tests will be dismissed from the screening visit without payment, except in the event they can produce a current, valid prescription for the medication that caused them to fail the drug test. Participants will also receive \$25 for completing the training session, \$25 for the camera return visit plus \$25 if they returned complete and useable photos within one week of the training session, \$100 for the fMRI session, \$30 for each post-quit lab visit (\$120 total) and a \$100 at the end of the study if they complete all sessions (up to \$420 total). Participants may also earn \$5.50 each day they complete their MetricWire surveys and GPS logging, with a \$75 bonus for 4 weeks compliance with GPS tracking and MetricWire surveys.(up to \$229). Participants will also receive \$10 for completing a 6 month post quit date follow-up phone call. Participants that decide to withdraw from

the study before fulfilling all of the requested tasks will be given compensation for completed study tasks.

DATA AND SAFETY MONITORING

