At the initial session, study staff will log participants into the MetricWire app using a unique username and password. This username and password will be set by the study staff and will contain no identifying information. All smartphone electronic diaries and ecological momentary assessments will be treated as confidential.

Use of a personal phone: Participants who choose to use their personal smartphone for the study will receive instructions on how to install the app on their phone and study staff will assist with the installation. The study team will also provide instructions on how to remove the app from their device at the end of the study. Thus, while we acknowledge that a breach of confidentiality is possible, the likelihood is very low.

[name] at UPMC will be a collaborator for the study. She is listed as outside key personnel and will not have access to any study PHI or identifiable information.

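### Days to lapse and days to relapse are censored outcomes, but the plan correlates them with brain response without defining the events, the end of follow-up or how participants with no event enter the analysis

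*Combined protocol and SAP*

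**What the plan says.** The Data Analysis section of the combined protocol and SAP gives one sentence on brain response and cessation: "We will examine correlation between brain responses to smoking environments (minus non-smoking environments) and smoking cessation outcomes (i.e. days to lapse, days to relapse". No section defines lapse or relapse, names the last day on which either can count, or gives a rule for participants who have neither event or are lost.

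The sources of smoking information are these:

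- **App (MetricWire Mobile Application).** "Participants will also be asked fill out a survey on the app each time they smoke a cigarette". No stop date is given. Payment is "for each of the 6 prompted surveys completed", so it does not depend on the per-cigarette reports.
- **Period of momentary assessment (Purpose).** Ratings are collected "over the course of 2 weeks before quitting smoking and 2 weeks after quitting smoking". The compensation section adds a "bonus for 4 weeks compliance with GPS tracking and MetricWire surveys".
- **App removal (Use of a personal phone).** "The study team will also provide instructions on how to remove the app from their device at the end of the study".
- **Lab visits at weeks 1, 2, 6 and 10.** At each, "the following will be collected: vitals (heart rate, blood pressure and weight), breath CO and measures of smoking withdrawal and mood". No dated smoking history is listed.
- **Six-month call.** It asks about present smoking and dependence, not about dates.

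The sample is described as recruitment "in order to identify 48 who meet all inclusion and exclusion criteria and complete all aspects of the study".

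**The concern.** Time to a first cigarette, or to relapse, is right-censored for anyone still abstinent at the last contact or lost before it. A correlation coefficient needs a number for every person, so the analyst must either leave these people out or assign them a day. The sentence permits both, and the two choices are far apart in what they can detect. Leaving out non-lapsers discards the contrast between people who lapse and people who do not, which carries much of the information.

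This is the only stated analysis that links the scanner measure to cessation outcome. If its rule is chosen after the data are seen, the result depends on that choice.

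A second question follows. If the one record that dates a cigarette ends about two weeks after quitting, later events have no date, and the end of follow-up cannot be set without knowing this.

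**Working it through.** **No figure to reproduce.** The plan gives no power, effect size, significance level or expected lapse rate for this analysis. Everything below except the 48 and the visit days is assumed.

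**Inputs.** N = 48 (Design and Procedures). Visits at days 7, 14, 42 and 70 (Lab Visits). Assumed: brain response x is standard normal, the hazard ratio is 1.5 per SD, the test is two-sided at 5%, 20% or 50% are lapse-free at day 70, and lapse dates are complete to day 70.

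**Model.** The cumulative hazard is c·(t/70)^k·1.5^x with k = 1.0 or 0.6. The constant c is solved so that the average of exp(−c·1.5^x) over x equals 0.20 or 0.50.

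**People without an event at day 70.** 48 × 0.20 = 9.6, about 10. 48 × 0.50 = 24.

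**Simulated power for first lapse, across those settings:**

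| Handling of non-lapsers | Power |
|---|---|
| Dropped, Pearson | about 6–21% |
| All set to day 70, Pearson | about 42–64% |
| Censored at day 70, Cox | about 48–68% |

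Repeat runs moved the ends of these ranges by a point or two. Taking the ends in order, Cox exceeds dropping by 48 − 6 = 42 and 68 − 21 = 47 points. It exceeds the common day-70 rule by only 48 − 42 = 6 and 68 − 64 = 4 points.

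**Type I error.** With a hazard ratio of 1, each rule on its own rejects about 5% of the time. Taking the smallest p-value from four readings (drop or assign, day 14 or day 70) gave 11–15%. That is a reason to fix the rule in advance, not a fault of any one rule.

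**When dated records stop.** Daily pay is 6 × $0.50 + $2.50 = $5.50, and 28 × $5.50 + $75 = $229, the stated maximum. This fixes the paid prompts and GPS days at 28. It does not fix the per-cigarette reports, which are not what is paid for. The Purpose wording favours a stop near day 14; the open-ended app instruction and the removal of the app at study end leave later logging possible. If app dates do stop at day 14, the next contacts come 42 − 14 = 28 and 70 − 42 = 28 days later.

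**If dates stop at day 14.** Under the same assumptions, Cox cut at day 14 has 18–48% power, 20–35 points below Cox to day 70. The loss is 10–11 points if 70% lapse by day 14, and 2 points if 90% do. Relapse fares worse: with an assumed average delay of 7 or 28 days after lapse, only 3–35% would have relapsed by day 14.

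**Would recall at later visits restore this?** Gain in power points over the day-14 cut, with between-visit recall added:

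| Later lapses unreported | 20–50% lapse-free at day 70 | 70% lapsed by day 14 | 90% lapsed by day 14 |
|---|---|---|---|
| 0% | 20 to 35 | 9 to 10 | about 2 |
| 20% | 13 to 23 | −1 to 4 | 0 |
| 40% | 7 to 15 | −5 to 1 | −1 |

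**The case against.** The best defence is that correlation is used loosely for association throughout the document, and that a correlation need not be a poor test. If all participants share one end of follow-up and non-lapsers are placed there, the test holds its 5% level and loses only a few points to Cox. With 48 people who complete everything, early loss may hardly arise. The analysis is not the primary aim, and all the rates above are assumed.

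Much of this stands. A reader might infer that any correlation with these times is invalid; that is wrong, because the common cut-off is a valid test. A reader might also infer that the sponsor means to drop non-lapsers; nothing in the documents says so. Nor do the documents establish that dated smoking ends at day 14: the $229 sum limits paid prompts and GPS days only. The recall table shows that added recall questions are not a clear gain either.

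What the defence does not supply is the rule itself. The plan states no common cut-off and no event definition. Completing the study does not give an abstinent participant a day of lapse. The loose wording can be settled in a few sentences, but they have to be written.

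**Conclusion.** The point holds as a should-fix matter. A method that needs a value for everyone is stated for outcomes that some participants will not have, and the handling is left open. The serious risk lies in one permitted reading: on the assumed inputs, dropping non-lapsers leaves about 6–21% power, against 42–64% with a common day 70 and 48–68% with Cox. The levels depend on the assumed hazard ratio, lapse rates and complete dating to day 70, and would change with other values. The need for a rule does not depend on them.

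It would be too strong to infer that the study's main result or its error rate is compromised. The primary aim, brain response to personal versus standard environments, does not use these outcomes, and type I error is about 5% under any single rule fixed in advance. The stop date of app logging is an open question, not a demonstrated loss of data.

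**What to change.** 1. Define lapse and relapse, take quit day as time zero, and name one end of follow-up. The visits are named from quit day, but their windows are counted from the camera return visit. The six-month call is timed from study completion in one section and from the quit date in another. These need to be reconciled before any of them serves as an anchor.
2. Replace the correlation with a time-to-event model, for example Cox regression with brain response as predictor. Include every scanned participant who starts the quit attempt, not only the 48 completers. Censor non-lapsers and losses at the last contact that gave smoking information, and state that non-lapsers are not dropped. Add a sensitivity analysis that counts loss as lapse.
3. State when per-cigarette app logging stops. If that is before week 10, end the exactly dated outcome there and say so. A dated recall question at the existing week 6 and week 10 visits is optional, since under-reporting can remove its gain.

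The cost is a few sentences of analysis plan and, if recall is chosen, one or two questions at visits that already take 20–30 minutes. The downsides are the proportional-hazards assumption, which should be checked, and loss that may be informative, which the sensitivity analysis addresses only in part.
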